## Protocol amendment summary

### Document history

Document	Date	Type of protocol amendment
Amendment 3 (substantial)	31-Jan-2022	Global
Amendment 2 (non-substantial)	17-Nov-2021	Global
Amendment 1 (substantial)	07-May-2021	Global
Original protocol	12-Mar-2021	NA

**Abbreviations:** NA = not applicable.

Note that protocol amendment summary of changes tables for the previous amendments are provided in [Appendix10](#).

### Amendment 3 (31-Jan-2022)

This amendment is considered to be substantial based on the criteria set forth in Article 10(a) of Directive 2001/20/EC of the European Parliament and the Council of the European Union or subsequent regulation.

### Overall rationale for the amendment

The main purpose for this protocol amendment is to change the event of a positive SARS-CoV-2 test (COVID-19) from leading to permanent discontinuation of IMP (Section [10.2.1](#)) to leading to a possible temporary discontinuation of IMP (Section [10.2.2](#)).

At the time of protocol preparation, COVID-19 was considered a disease with lower respiratory tract involvement in many people infected. However, even though the IL-22R is expressed in the lungs, the role of LEO 138559 in the context of COVID-19 disease was unknown. It was expected that the number of people infected with SARS-CoV-2 during the conduct of the trial would be low, and therefore not anticipated to affect data integrity of the trial. These assumptions led to a conservative approach of permanently discontinuing IMP for subjects testing positive for SARS CoV-2.

During trial conduct, the COVID-19 situation in many countries including Germany, Poland, US, and Canada, has changed. At the beginning of the pandemic, the number of infected patients was lower than now, but with a higher risk of severe illness. Now, a very high number of newly infected people each day is observed (possibly due to a combination of more contagious mutations and a higher test capacity), but with an overall lower number of patients with severe illness (possibly due to the introduction of vaccines and virus variants leading to

THIS DOCUMENT CONTAINS CONFIDENTIAL INFORMATION AND MUST NOT BE COPIED OR MADE AVAILABLE TO ANY THIRD PARTY WITHOUT THE PRIOR WRITTEN CONSENT OF THE LEO PHARMA GROUP

milder symptoms in the majority of the infected people). Based on this, a potential safety concern for the patients in relation to SARS CoV-2 infection is now reduced.

The observed development in the SARS CoV-2 infection rates, results in a risk of a potential higher trial attrition rate than previously expected. With the current knowledge of COVID-19 disease course, presenting with many cases of mild disease, it is considered reasonable to not per default discontinue subjects with a SARS CoV-2 infection from IMP treatment. Based on local guidelines and regulations on handling of SARS CoV-2 infection, it is considered relevant to allow temporary, instead of per default permanent discontinuation of IMP similar to other COVID-19 related disruptions (Section 10.2.2 and Appendix 9). Note that as per investigator discretion, the IMP can still be permanently discontinued.

Introducing this amendment increases the possibility of retaining patients in the trial, thereby fulfilling our ethical obligation to all the participating subjects and investigators. Furthermore, the amendment does not affect the total number of subjects, statistical analysis, and interpretation of the trial results, and has no impact on patient safety, thus no impact on the scientific value or integrity of the trial.

All changes to the protocol are presented in the summary of changes table below except for a few minor editorial changes (e.g. spelling errors).

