## 14 Statistical methods

### 14.1 Sample size

At baseline, a total of 52 subjects will be randomised 1:1:

- 26 subjects to LEO 138559 450 mg Q2W.
- 26 subjects to placebo Q2W.

The sample size is determined using t-test for pairwise consideration of 2 treatment groups based on the following assumptions:

Treatment	Expected reduction in EASI (SD)*	Attrition rate
LEO 138559	22.9 (13)	30%
Placebo	7.3 (18)	30%

\*Expected reduction in EASI for LEO 138559 is based on results from an upadacitinib phase 2b trial (28), and for placebo, the expected reduction is based on a dupilumab phase 2b trial (58).

With a significance level of 5%, 18 subjects per treatment group will provide a nominal power of at least 80% to detect a difference between the 2 treatment groups. Assuming a maximum attrition rate of 30%, 26 subjects in each treatment group should be randomised into the trial.

Assuming a screening failure rate of 35%, the planned number of subjects to screen is set to 80.

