## 14.3 Statistical analysis

### 14.3.1 General principles

All significance tests will be two-sided using the 5% significance level. All confidence intervals will be presented with 95% degree of confidence, unless otherwise specified. Efficacy analyses will be based on the FAS, and safety analyses will be based on the safety analysis set. PK analysis will be based on the PK analysis set.

If not mentioned otherwise, endpoints will be summarised descriptively at each visit by treatment. For endpoints evaluated over time, plots will be made to explore the trajectories with time.

An observed cases approach will be used for tabulations of data by visit (that is, involving only those subjects who attended each specific visit). For categorical endpoints, the number of subjects not attending each specific visit will also be provided.

Categorical data will be summarised by treatment group, using the number and percentage of subjects in each category. Continuous data will be summarised using the mean, median, standard deviation (SD), 1st quartile, 3rd quartile, minimum, and maximum values.

Additionally, geometric mean and coefficient of variation (CV) will be provided for the PK endpoint.

In general, for endpoints evaluated as change from baseline and/or where a baseline adjustment is applied, baseline is defined as assessments conducted at the randomisation visit (Visit 3), if not otherwise stated. If the information is not available at the randomisation visit but at the (re)screening visit (Visit 1) then this will be used instead.

All the analyses specified in the protocol will be reviewed in relation to the blinded data actually obtained, and the statistical analysis plan will be finalised before breaking the randomisation code.

Any changes from the statistical analyses planned in this clinical trial protocol will be described and justified in a protocol amendment, the statistical analysis plan, and/or in the CTR, dependent on the type of change.

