### 14.3.2 Handling of missing values

The methods for handling of missing values for the primary endpoint are described in Section 14.3.8.

THIS DOCUMENT CONTAINS CONFIDENTIAL INFORMATION AND MUST NOT BE COPIED OR MADE AVAILABLE TO ANY THIRD PARTY WITHOUT THE PRIOR WRITTEN CONSENT OF THE LEO PHARMA GROUP

For other continuous endpoints for which a MMRM analysis will be used it will be assumed that data is missing at random within each treatment group. The missing data will be predicted by the MMRM model.

For the categorical endpoints for which a CMH test will be used, subjects with missing data will be considered as non-responders and their missing values will be imputed using NRI.

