### **14.3.3 Handling of intercurrent events related to the COVID-19 pandemic**

As the implications of the COVID-19 pandemic might, extraordinarily, influence trial events and data in manners not foreseen by the clinical trial protocol, this section introduces the statistical considerations for handling of intercurrent events related to the pandemic for the primary endpoint.

A supplementary estimand, ‘pandemic-modified composite’, is introduced for analysis of the primary endpoint to address permanent discontinuation of IMP due to the pandemic as an intercurrent event. Details are described in Section [14.3.8](#).

Interruption of IMP administration during the treatment period (Weeks 0–16) is not considered as an intercurrent event if only 1 full dose (450 mg) is missed. Observed data from subjects missing more than one dose will be ‘treated as missing’. The causal relationship of permanent discontinuation of IMP related to the pandemic will be recorded in the eCRF.

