### 14.3.10 Analysis of exploratory efficacy endpoints

#### Binary endpoints

The following endpoints;

- Having a decrease in EASI of at least 50% (EASI 50) from baseline to Week 16.
- Having a decrease in EASI of at least 75% (EASI 75) from baseline to Week 16.
- Having a decrease in EASI of at least 90% (EASI 90) from baseline to Week 16.
- Having vIGA-AD of 0 (clear) or 1 (almost clear) at Week 16.

will be analysed using CMH test stratified by region and baseline disease severity. Subjects who received rescue treatment prior to the Week 16 visit or permanently discontinued IMP or have missing data will be considered as non-responders. Additionally, responder rates will be summarised descriptively at each visit by treatment group.

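### Responder endpoints count pandemic-related IMP stops and pandemic-missed Week 16 visits as treatment failure, although the plan treats such losses as uninformative about efficacy in three of its four primary-endpoint estimands

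*Combined protocol and SAP*

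**What the plan says.** **Responder scoring.** For EASI 50/75/90 and vIGA-AD 0/1, Section 14.3.10 states: "Subjects who received rescue treatment prior to the Week 16 visit or permanently discontinued IMP or have missing data will be considered as non-responders". Section 14.3.2 gives the general rule for endpoints tested by CMH: "subjects with missing data will be considered as non-responders and their missing values will be imputed using NRI". Section 14.3.11 sends the itch responders to the same test. None of the three sections separates pandemic causes from others.

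**Pandemic handling.** Section 14.3.3 announces its scope as "handling of intercurrent events related to the pandemic for the primary endpoint". Its subsection on affected data calls for MAR imputation without naming an endpoint, but it sits inside that scope and refers to the primary-endpoint estimands for detail. Section 14.3.8 defines a pandemic stop as one not attributed to lack of efficacy. Panel 13 assigns it MI under MAR in the hypothetical, pandemic-modified composite and treatment policy estimands, and LOCF in the composite one.

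**The COVID-19 rule over time.** The Amendment 3 rationale describes the position until 31-Jan-2022: "These assumptions led to a conservative approach of permanently discontinuing IMP for subjects testing positive for SARS CoV-2". The change table shows that the replaced text of Appendix 9 also withdrew such subjects from the trial. Section 10.2.2 and Appendix 9 now allow a temporary hold. The rationale concludes that "the amendment does not affect the total number of subjects, statistical analysis, and interpretation of the trial results".

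**The concern.** A subject who was responding well and was taken off IMP because of a positive test is a treatment failure on every Week 16 responder endpoint. Because the replaced rule also withdrew the subject from the trial, there would normally be no Week 16 assessment either. The same infection after the amendment may lead only to a hold, and the subject can then be counted as a responder. A Week 16 visit lost to local restrictions is also a failure, since phone visits may not be used for efficacy assessments (Section 5.5, Appendix 9).

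The plan therefore takes two views of one event. For the primary endpoint it mostly treats the event as carrying no efficacy information. For the responder endpoints it treats it as failure. In a small proof-of-concept trial, readers will set the responder rates beside the primary result, and the two could diverge for a reason unrelated to the drug.

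**Working it through.** **1. The plan's own figure.** The documents give a sample size only for EASI change (Section 14.1). Difference = 22.9 − 7.3 = 15.6. SD = √((13² + 18²)/2) = 15.70. Noncentrality with 18 per arm = 15.6 / (15.70 × √(2/18)) = 2.98 on 34 df. Two-sided 5% t-test power = 82.5%, which agrees with the stated minimum of 80%. Allowing for 30% attrition, 18/0.70 = 25.7, so 26 per arm. The figure reproduces. No power or response rate is stated for any responder endpoint.

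**2. The rules side by side.**

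| Event | Primary endpoint (Panel 13) | Week 16 responders (14.3.2, 14.3.10, 14.3.11) |
|---|---|---|
| Pandemic-related permanent stop | MI under MAR in 3 of 4 estimands | Non-response |
| Week 16 missing because of the pandemic, no intercurrent event | MI under MAR in 3 of 4 estimands | Non-response |

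**3. Effect on the responder difference.** Let p1 and p0 be the true response rates (active, placebo). Let q1 and q0 be the fractions lost to the pandemic, with loss unrelated to response. Under NRI the expected difference is p1(1 − q1) − p0(1 − q0).

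- If q1 = q0 = q, this is (1 − q)(p1 − p0). One subject per arm of 26 gives q = 1/26 = 3.8%.
- In general it shrinks only if p1·q1 > p0·q0.

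**4. Illustrations.** The rates and counts below are assumptions. From the documents: "At baseline, a total of 52 subjects will be randomised 1:1", hence 26 per arm, and "All significance tests will be two-sided using the 5% significance level". Power is by exact enumeration of the unstratified Mantel-Haenszel chi-square test. NRI multiplies each response rate by (1 − q). MAR is approximated by dropping the affected subjects (24 or 22 per arm at the true rates).

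| True rates | Affected per arm | Expected NRI difference | Power, NRI | Power, MAR approx. | Power, no loss |
|---|---|---|---|---|---|
| 60% v 20% | 2 | 36.9 points (from 40) | 80.6% | 84.4% | 85.1% |
| 60% v 20% | 4 | 33.8 points | 75.2% | 79.1% | 85.1% |
| 50% v 15% | 2 | 32.3 points (from 35) | 73.8% | 76.7% | 79.2% |
| 50% v 15% | 4 | 29.6 points | 67.8% | 71.6% | 79.2% |

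Under these assumptions MAR handling removes the expected shrinkage and recovers about 3 to 4 points of power.

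**5. Unequal losses.** At 40% v 10%:

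- q1 = 5%, q0 = 20%: 0.40 × 0.95 − 0.10 × 0.80 = 0.30, unchanged.
- q1 = 0, q0 = 10%: 0.40 − 0.09 = 0.31, wider.

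Even with an equal underlying loss of 7.7% (2/26), chance decides the realised result. At 40% v 10% the difference shrinks in 49% of trials, is unchanged in 43% and widens in 9%.

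**The case against.** Three stronger readings are tempting, and the documents support none of them.

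- **That Amendment 3 causes the problem.** The scoring rule is in Sections 14.3.2 and 14.3.10. The amendment's change table alters nothing in Section 14, so its statement about statistical analysis is literally true. By allowing a hold it also reduces forced failures. What remains is a before/after difference in how one event is scored, which bears on interpretation only.
- **That every responder difference must shrink.** Shrinkage is an expectation under balanced, response-independent loss (working, step 5).
- **That the rationale's remark on very high infection numbers sizes the effect.** It refers to people newly infected each day in many countries at the time of the amendment, and says that numbers were lower earlier. It does not count trial subjects.

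Other objections carry weight. The endpoints are exploratory (Panel 3), p-values are nominal (Section 14.3.7), and no decision rests on responder power. All-cause NRI is a legitimate composite definition, and the first supplementary estimand likewise carries pandemic losses forward. MAR is not assured either. Sections 5.5 and 12.2 raise a theoretical infection risk from blocking IL-22R, although Section 5.5 does not expect a higher risk of viral infection. If infection depended on treatment, NRI would be the cautious choice. This supports keeping NRI in the report. It does not support NRI as the only analysis when the plan's own definition separates these stops from lack of efficacy.

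**Conclusion.** The inconsistency is real and of modest weight. Pandemic-related permanent stops, including those required before Amendment 3, and pandemic-missed Week 16 visits are scored as failure on the responder endpoints, while three of four primary-endpoint estimands impute them.

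If losses are balanced and unrelated to response, the expected difference falls by the fraction affected, 3.8% of its value per affected subject per arm. With unequal losses the direction is open. The absolute size cannot be stated, because the documents give neither the number affected, nor its split by arm, nor responder rates.

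Two limits apply. For itch response before Week 16, the text does not say whether a later stop counts against an earlier visit, so this conclusion covers Week 16 only. A temporary hold with more than one missed dose is treated as missing under Section 14.3.3, and whether that reaches the responder endpoints is not stated. A post-amendment infection is therefore not certain to stay evaluable.

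**What to change.** In Sections 14.3.10 and 14.3.11, or in the SAP before the code is broken, add an analysis of Week 16 EASI 50/75/90, vIGA-AD 0/1 and itch response that:

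- treats data after a pandemic-related permanent stop, and data missing because of the pandemic, as missing and imputes them by MI under MAR within arm;
- derives the EASI responders from the first-step imputed EASI datasets of the second supplementary estimand, before LOCF is applied;
- keeps non-response for rescue, non-pandemic discontinuation and other missing data;
- names the imputation model for vIGA-AD and itch, since a logistic model with about 26 per arm can fail when responders are few;
- states how the stratified results are pooled, for example by Rubin's rules on the Mantel-Haenszel risk difference.

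Report the all-NRI analysis alongside. Tabulate pandemic-related losses by arm and by before/after Amendment 3. Limit the rationale's statement on interpretation to the primary analysis.

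The cost is text and some programming. No new data are needed, because the eCRF already records the pandemic cause (Sections 10.2.1 and 14.3.3, Appendix 9). The downside is that responder rates become slightly less conservative and rest on MAR for a few subjects.

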## Summary of changes

Section no. and name	Description of change	Brief rationale
Section 9.10 Reporting product complaints	[contact] [name]	Editorial.
Section 10.2.1 Reasons for permanent discontinuation of IMP	<del>Infection with SARS CoV 2 (COVID-19)</del>	Due to change in the global SARS CoV-2 (COVID-19) situation.
Section 10.2.2 Reasons for temporary discontinuation of IMP	• COVID-19 related disruption <del>leading to site closure</del>	Due to change in the global SARS CoV-2 (COVID-19) situation.
Section 13.4.1 Investigator reporting responsibilities	[contact] [name]	Editorial.
Appendix 3C Subject and data confidentiality	Processing of personal data on behalf of LEO Pharma requires a written agreement between LEO Pharma and the relevant party which covers collection, processing, and transfer of personal data in the clinical trial as well as reporting obligations in the event of any data breach . In certain cases, an agreement on transfer of personal data may also be required.	Editorial.

THIS DOCUMENT CONTAINS CONFIDENTIAL INFORMATION AND MUST NOT BE COPIED OR MADE AVAILABLE TO ANY THIRD PARTY WITHOUT THE PRIOR WRITTEN CONSENT OF THE LEO PHARMA GROUP

Section no. and name	Description of change	Brief rationale
Appendix 9 COVID-19 pandemic contingency plan	<del>A subject testing positive for COVID-19 after randomisation must be permanently discontinued from IMP and withdrawn from the trial. A subject testing positive for COVID-19 after randomisation may be temporarily discontinued from IMP. IMP treatment may be reinstated at the investigator's discretion.</del>	Due to change in the global SARS CoV-2 (COVID-19) situation.
Appendix 10 Protocol amendment history	Protocol amendment 2, Summary of changes table moved to Appendix 10 .	Editorial.
Appendix 10 Protocol amendment history	Amendment 2 (197-Nov-2021)	Editorial.

THIS DOCUMENT CONTAINS CONFIDENTIAL INFORMATION AND MUST NOT BE COPIED OR MADE AVAILABLE TO ANY THIRD PARTY WITHOUT THE PRIOR WRITTEN CONSENT OF THE LEO PHARMA GROUP

## List of abbreviations

AAD	American Academy of Dermatology
Ab	antibody
AD	atopic dermatitis
ADA	anti-drug antibodies
AE	adverse event
AESI	adverse event of special interest
ANCOVA	analysis of covariance
anti-HBc	hepatitis B core antibody
anti-HBs	hepatitis B surface antibody
BCC	basal cell carcinoma
BP	blood pressure
BMI	body mass index
BSA	body surface area
CCL17	chemokine (C-C motif) ligand 17
CDISC	Clinical Data Interchange Standards Consortium
CI	confidence interval
CMH	Cochran–Mantel–Haenszel
CMO	contract manufacturing organisation
CONSORT	Consolidated Standards of Reporting Trials
COVID-19	coronavirus disease 2019
CPM	clinical project manager
CRA	clinical research associate
CRO	contract research organisation
CTR	clinical trial report
DLQI	Dermatology Life Quality Index
DPP4	dipeptidyl peptidase-4
EASI	Eczema Area and Severity Index
EASI 50	at least 50% reduction in EASI score
EASI 75	at least 75% reduction in EASI score
EASI 90	at least 90% reduction in EASI score
ECG	electrocardiogram
eCRF	electronic case report form

THIS DOCUMENT CONTAINS CONFIDENTIAL INFORMATION AND MUST NOT BE COPIED OR MADE AVAILABLE TO ANY THIRD PARTY WITHOUT THE PRIOR WRITTEN CONSENT OF THE LEO PHARMA GROUP

eDiary	electronic diary
EMA	European Medicines Agency
ePRO	electronic patient-reported outcome
EU	European Union
FAS	Full analysis set
Fc	fragment crystallisable
FDA	United States Food and Drug Administration
FiM	first in man
FSFV	first subject first visit
GCP	Good Clinical Practice
GINA	Global Initiative for Asthma
HbsAg	hepatitis B surface antigen
HCP	healthcare professional
HIV	human immunodeficiency virus
HRQoL	health-related quality of life
ICF	informed consent form
ICH	International Council for Harmonisation of Technical Requirements for Pharmaceuticals for Human Use
ID	identification number
IEC	independent ethics committee
IFN- $\gamma$	interferon gamma
IGA	Investigator's Global Assessment
IgE	immunoglobulin E
IgG	immunoglobulin G
IgM	immunoglobulin M
IL	interleukin
IL-10R2	interleukin 10 receptor 2
IL-22BP	interleukin 22 binding protein
IL-22R	interleukin 22 receptor
IL-22R1	interleukin 22 receptor 1
IL4Ra	interleukin 4 receptor a
IMP	investigational medicinal product
IND	Investigational New Drug

THIS DOCUMENT CONTAINS CONFIDENTIAL INFORMATION AND MUST NOT BE COPIED OR MADE AVAILABLE TO ANY THIRD PARTY WITHOUT THE PRIOR WRITTEN CONSENT OF THE LEO PHARMA GROUP

IRB	institutional review board
IRT	interactive response technology
IUD	intrauterine device
IUS	intrauterine hormone-releasing system
IV	Intravenous(ly)
JAK	janus kinase inhibitor
JP	Japan
KLH	keyhole limpet hemocyanin
LEO 138559	investigational medicinal product investigated in this trial
LOCF	last observation carried forward
LS	least squares
mAb	monoclonal antibody
MAD	multiple ascending dose
MAR	missing at random
MedDRA	Medical Dictionary for Regulatory Activities
MI	multiple imputation
MMRM	mixed model repeated measures
MoA	mode of action
NA	not applicable
NCT	National Clinical Trial
NOAEL	no-observed-adverse-effect level
NRI	non-responder imputation
NRS	numeric rating scale
PCR	polymerase chain reaction
PD	pharmacodynamics
PDE-4	phosphodiesterase-4
PEF	peak expiratory flow
PK	pharmacokinetics
PoC	proof of concept
POEM	Patient-Oriented Eczema Measure
PPD	purified protein derivative
PRO	patient-reported outcome
Q2W	every second week

THIS DOCUMENT CONTAINS CONFIDENTIAL INFORMATION AND MUST NOT BE COPIED OR MADE AVAILABLE TO ANY THIRD PARTY WITHOUT THE PRIOR WRITTEN CONSENT OF THE LEO PHARMA GROUP

qPCR	Quantitative polymerase chain reaction
QT	QT interval, time from start of the Q wave to the end of the T wave on an ECG tracing
RNA	ribonucleic acid
rRNA	ribosomal RNA
SAD	single ascending dose
SAE	serious adverse event
SARS-CoV-2	severe acute respiratory syndrome coronavirus 2
SC	Subcutaneous(ly)
SCC	squamous cell carcinoma
SD	standard deviation
SDTM	standard data tabulation model
SOC	system organ class
STAT	signal transducer and activator of transcription
SUSAR	suspected unexpected serious adverse reaction
TARC	thymus and activation-regulated chemokine
TCI	topical calcineurin inhibitor(s)
TCS	topical corticosteroid(s)
Th2	T-helper 2
TMDD	target-mediated drug disposition
US	United States of America
vIGA-AD	Validated Investigator Global Assessment Scale for Atopic Dermatitis
WOCF	worst observation carried forward

THIS DOCUMENT CONTAINS CONFIDENTIAL INFORMATION AND MUST NOT BE COPIED OR MADE AVAILABLE TO ANY THIRD PARTY WITHOUT THE PRIOR WRITTEN CONSENT OF THE LEO PHARMA GROUP

